## **11. Risks and Benefits**

### **11.1 Potential Risks**

Medtronic follows rigorous Quality Assurance and Control procedures throughout the lifecycle of a product, from the business analysis phase through development, market release, and post-market surveillance. The risk analysis process for the LINQ™ for COPD study is being performed in accordance with ISO 14971, and ensures that the level of residual risk is reduced to as low as possible prior to starting the clinical study.

There are potential risks and side effects associated with a Reveal LINQ™ device implant and explant procedures:

- Allergic reaction or device rejection phenomena including local tissue reaction
- Excessive device migration (internal pocket device movement as well as device externalization)
- Pocket infection
- Erosion through the skin
- Tissue / vascular trauma

Possible additional risks for participating in this study include the following (although others are possible):

- The Reveal LINQ™ device with investigational RAMware download is investigational and may be no more effective or less effective than a commercially available Reveal LINQ™ device system.
- There may be stimulation effects from the impedance measurements being taken across the Reveal LINQ™ device electrodes. The amount of current injected as part of the impedance measurements has been minimized to very low levels to prevent patient harm.
- The investigational RAMware feature set will cause current drain on the Reveal LINQ™ ICM device battery. Risk control measures have been implemented and the current projected longevity of a LINQ™ device with investigational RAMware shows a 5 month decrease in average

projected service life compared to a LINQ™ device without the RAMware. The exact service life of the LINQ™ device will vary depending on each subject's use.

- There may be undesired device interactions with the investigational RAMware, potentially resulting in loss of or inaccurate Reveal LINQ™ data, and/or premature explant. Once the investigational RAMware feature set is executed, periodic data integrity checks are in place to ensure correct functionality.
- The Reveal LINQ™ device with the investigational RAMware download may present data that are different than anticipated due to unknown circumstances or medical conditions.
- There may be other discomforts and risks related to the Reveal LINQ™ device with investigational RAMware download and/or this study that are not foreseen at this time.

## 11.2 Risk Minimization

As referenced above, the potential risks associated with the LINQ™ HF and ALLEViate-HF investigational RAMware were identified, assessed, evaluated and effectively controlled. Any potential risks associated with this study are further minimized by selecting qualified investigators and training study personnel on the Clinical Investigation Plan.

In addition, investigators will be actively involved in the implantation and regular follow-up of the subjects implanted with the Reveal LINQ™ with investigational RAMware systems. At each office follow-up visit required per protocol (Table 3: Data collection and study procedure requirements at subject visits), the Reveal LINQ™ device will be interrogated, device data collected to verify appropriate device function and patient's health assessed for any adverse events.

Medtronic is further minimizing the possibility of risks by performing required laboratory and pre-clinical testing prior to the clinical study, implementing quality control measures into production processes, providing guidelines for subject selection and evaluation, and providing adequate instructions and labeling.

**Table 8: Potential Risks and Risk Minimization**

Potential Risk	Minimization
ICM Pocket Infection from implant/explant procedure or over duration of implant	

• Adherence to international standards for sterility of implanted products

• The product packaging designed to protect device sterility

• The insertion procedure and tools are designed to be minimally invasive

• Wound check following implant, per site's practice

# Reveal LINQ™ for COPD Study Clinical Investigation Plan

Version 5.0,  
1-DEC-22

Page 48 of 79

Medtronic

Potential Risk	Minimization
Allergic reaction or ICM Rejection following implant procedure	

Assessment of subjects to ensure no Allergic or rejection reaction to materials used in incision/insertion tools, Reveal LINQ™ ICM exterior or incision closure method

Wound check following implant, per site's practice

Close monitoring with follow-up appointments

Investigator discretion to remove ICM and report study deviation

Use of biocompatible materials in the Incision/ Insertion Tools and Reveal LINQ™ ICM exterior patient-contacting surfaces

Excessive ICM Migration following implant procedure (internal device movement and externalization)	

Training and Information for User on the Reveal LINQ™ implant technique and incision closure techniques

Use of the implant tools to create small incision and tight pocket

Wound check following implant, per site's practice

Investigator discretion to remove if deemed medically necessary

IFUs (Instructions for Use) provide information regarding medical procedures and activities which may interact with the ICM.

Reveal LINQ™ ICM design includes anti-migration features on the header

Blunt Tissue Injury/Tissue or Vascular Trauma, bleeding from implant/ explant procedure	

The ICM and implant procedure are designed to be minimally invasive.

Insertion Tool has a stop position that prevents insertion of the probe beyond the distance required for implant.

Training on the correct use of implant tools

Selection of experienced investigators

Pain, Scarring from implant/explant procedure or implanted device	

The shape and small device size minimize the invasiveness of the implant and explant procedures, and the discomfort patients may experience from having an ICM.

Use of incision tool will produce the smallest incision possible for implant

Toxicity risks due to ICM battery	

Battery and device and hermeticity and reliability requirements prevent leakage of toxic substances.

**Medtronic Business Restricted**

**CONFIDENTIAL**

056-F275 Rev E Clinical Investigation Plan Template

# Reveal LINQ™ for COPD Study Clinical Investigation Plan

Version 5.0,  
1-DEC-22

Page 49 of 79

Medtronic

Potential Risk	Minimization
Premature/Unexpected ICM explant /revision	

The projected longevity of a Reveal LINQ™ device with investigational RAMware shows a 5 month decrease in average projected service life compared to a LINQ™ device without the RAMware. The exact service life of the LINQ™ device will vary depending on each subject's use.

Electromagnetic interference	

Design consideration and precautions in place for the Reveal LINQ™ system remain effective to address EMI risks

Information regarding EMI (possible sources and ways to reduce interference) is provided to the user

The system adheres to international standards for the production of RF energy, reducing the probability of interference with other equipment.

Pain or stimulation due to electrical currents or ICM heating	

Design controls in place to protect against leakage currents in normal and fault conditions

Design controls are in place to protect against device heating in normal and fault conditions.

The amount of current injected as part of the impedance measurements has been minimized to prevent subject harm

Missing/Misleading information causing inappropriate medical intervention	

The system uses data integrity checks to detect data corruption and notify the clinician

The system ensures components are compatible with the system components; the instructions for use provide guidance on maintenance of the system (e.g., software/app updates)

The system provides notifications to the clinician regarding system status (e.g., patient transmissions, battery status)

Injury due to mechanical device failure	

Mechanical device integrity requirements were implemented and verified. They have been validated against the expected use conditions.

Security vulnerability impacting device settings, data integrity, communications, or longevity	

The system uses encrypted communication to transfer data

The system detects unauthorized messages and takes actions to protect itself.

Denial of access to medical therapy or diagnostic	

The ICM is MRI conditional

The system provides information about the compatibility of the ICM with common medical procedures

The system provides means to non-invasively identify the ICM, so its compatibility can be verified prior to the procedure.

Failure to seek necessary medical attention	

Instructions for use warns users against use of the ICM system as a real-time / emergency monitoring system.

**Medtronic Business Restricted**

**CONFIDENTIAL**

056-F275 Rev E Clinical Investigation Plan Template

# Reveal LINQ™ for COPD Study Clinical Investigation Plan

Version 5.0,  
1-DEC-22

Page 50 of 79

Medtronic

Potential Risk	Minimization
Removal and disposal of system components (biohazards, environmental/property damage hazards)	

The insertion tools are designed to be easily disposed of

The IFU provides guidance on disposal of the ICM at the end of service

Undesired device interactions with the investigational RAMware	

Device interactions analysis to ensure there are no undesired interactions between the investigational RAMware and the Reveal LINQ™ device firmware.

The investigational RAMware is designed to be automatically removed by the ROM code during POR processing

There may be a concern for electrical or electromagnetic interference between the LINQ™ device and the other associated study equipment. Among the systems that have the potential for electromagnetic interference, here are the associated frequencies and characteristics:

- LINQ™ – transmits and receives Telemetry B signal frequencies for communication with programmer
- DR220 Holter – receives Telemetry B signal frequencies for recording
- MyCareLink Home Monitor – receives Telemetry B signal frequencies from LINQ and transmits data to the CareLink Network using 3G cellular frequencies
- Emfit bed monitor – the sensor component uses passive electrical signals to collect motion from the ribbon. No electrical signal is transmitted to take a measurement. The data is then transmitted from the communication hub using 3G cellular frequencies

It appears that there should not be any electromagnetic interference from transmission by any of the planned study equipment. However, should it occur, electromagnetic interference can be mitigated by user intervention, such as positioning devices to minimize interference.

There may be additional discomforts and risks associated with the Reveal LINQ™ device or participation in this study that are not foreseen at this time.

## 11.3 Potential Benefits

The Reveal LINQ™ for COPD study may offer no direct personal benefit to individual subjects.

Subjects may benefit from continuous arrhythmia monitoring with the Reveal ICM, as this monitoring could result in diagnosis of Atrial Fibrillation (or other arrhythmias) and comprehensive evaluation of symptoms on an earlier and more conclusive basis than what would be possible without an implantable cardiac monitor. Subjects may also benefit from being evaluated more frequently in the office according to the study visit schedule.

**Medtronic Business Restricted**

**CONFIDENTIAL**

056-F275 Rev E Clinical Investigation Plan Template

The information gained from this study could result in the improved management of other patients receiving a Reveal LINQ™ device in the future. Additionally, information collected from this study may assist in the design of new product(s)/therapy(ies) and/or instructions for use.

## 11.4 Risk-Benefit Rationale

Since the differences between the Reveal LINQ™ market-released device and the Reveal LINQ™ device with the investigational RAMware download are minimal, both devices are used in accordance with the Reveal LINQ™ implant manual and/or user manual, as applicable. The risks associated with the device are similar as would be the case if the subject received a Reveal LINQ™ device outside the study context. The risks introduced by the investigational RAMware are being evaluated and risk control measures being implemented to reduce the risk to as low as possible to minimize patient harm.

The study requirements for careful physician selection and training, and in-office visits carry potential benefits that might not be present if the subject was not enrolled in the study. Hence, for individual subjects, participation in the study may have greater benefit than risk. Moreover, the value of the knowledge to be gained by conducting this clinical study could help in the diagnosis of future patients. Lastly, the prospective benefit to subjects of having Reveal LINQ™ cardiac monitoring, with the potential to diagnose life-threatening arrhythmias, may provide the patient significant clinical benefit.

## 12. Adverse Events and Device Deficiencies

Timely, accurate, and complete reporting and analysis of safety information for clinical studies are crucial for the protection of subjects. Reporting and analysis of safety data are mandated by regulatory authorities worldwide. Medtronic has established procedures in conformity with worldwide regulatory requirements to ensure appropriate reporting of safety information. This study will be conducted in accordance with these procedures and regulations.

### 12.1 Adverse Events

To ensure that all AEs that are potentially relevant are collected, the following subset of AEs will be collected throughout a subject's participation, starting at the time the informed consent form is signed:

- All Reveal LINQ™ Procedure related AEs
- All Reveal LINQ™ System related AEs
- All Serious AEs
- All Pulmonary related AEs
- All Cardiovascular related AEs

Reporting of AEs to Medtronic will occur on an Adverse Event e-CRF, including a description of the event, the diagnosis, the date of event onset, the date the site became aware of the event, the relatedness and seriousness of the event, diagnostic tests and procedures performed, actions taken as a

**Medtronic Business Restricted**

result of the event, and outcome of the event. Each AE must be recorded on a separate AE eCRF. Subject deaths are also required to be reported and should be collected on an AE CRF with a Fatal outcome. Refer to section 12.6 for subject death collection and reporting requirements.

Documented pre-existing conditions are not considered AEs unless the nature or severity of the condition has worsened post implant. In all geographies, unavoidable adverse events, listed in Table 9, need not be reported unless the adverse event worsens or is present outside the stated timeframe.

## 12.2 Device Deficiency

Device deficiency (DD) information will be collected throughout the study and reported to Medtronic. Reporting of DDs to Medtronic will occur on a device deficiency e-CRF. Note that DDs that result in an adverse device effect (ADE) to the subject should be captured on an AE CRF only. Device deficiencies that did not lead to an AE but could have led to a serious adverse device effect (SADE) (i.e., if suitable action had not been taken, if intervention had not been made, or if the circumstances had been less fortunate) require immediate reporting.

## 12.3 Processing Updates and Resolution

For any changes in status of a previously reported AE (i.e. change in actions taken, change in outcome, change in relatedness), an update to the original AE must be provided. All reported adverse events must be followed until the adverse event has been resolved, the subject exits the study or until study closure, whichever occurs first. At the time of study exit, all collected AEs with an outcome of “not recovered/not resolved”, “recovering/resolving” or “unknown” must be reviewed and updates provided as applicable.

## 12.4 Definitions/Classifications

Adverse event (AE) and device deficiency (DD) ISO 14155:2020 definitions are provided in Table below. Where the definition indicates “device”, it refers to any device used in the study. This might be the device under investigation, or any market released component of the system.

Table 9: Adverse Event and Device Deficiency Definitions

General	
Adverse Event (AE) (ISO 14155:2020 section 3.2)	Any untoward medical occurrence, unintended disease or injury, or untoward clinical signs (including abnormal laboratory findings) in subjects, users or other persons, whether or not related to the investigational medical device and whether anticipated or unanticipated.  NOTE: This definition includes events related to the investigational medical device or the comparator.  NOTE: This definition includes events related to the procedures involved. NOTE: for users or other

*Medtronic Business Restricted*

# Reveal LINQ™ for COPD Study Clinical Investigation Plan

Version 5.0,  
1-DEC-22

Page 53 of 79

Medtronic

	persons, this definition is restricted to events related to investigational medical devices. (ISO 14155:2020 section 3.2)
Adverse Device Effect (ADE) (ISO 14155:2020 section 3.1)	Adverse event related to the use of an investigational medical device. NOTE: This definition includes adverse events resulting from insufficient or inadequate instructions for use, deployment, implantation, installation, or operation or any malfunction of the investigational medical device. NOTE: This definition includes any event resulting from use error or from intentional misuse of the investigational medical device. NOTE: This includes 'comparator' if the comparator is a medical device.
Device Deficiency (DD) (ISO 14155:2020 section 3.19)	Inadequacy of a medical device with respect to its identity, quality, durability, reliability, safety or performance. Note: Device deficiencies include malfunctions, use errors, and inadequate labelling.
Relatedness	
Procedure Related	An adverse event that occurs that is directly related to the insertion or modification of the Reveal LINQ™ system.
System Related	An adverse event that results from the presence or performance of any component of the Reveal LINQ™ system (including the LINQ™ device, incision/insertion tools, patient assistant and programmer).
Pulmonary Related	An adverse event associated with the lungs in which signs and symptoms are experienced in either the upper or lower Respiratory systems (i.e. COPD, Pneumonia, Asthma, Bronchitis, etc.).
COPD Event	An adverse event where the underlying COPD condition exacerbates beyond normal day-to-day variations, where an increase in dyspnea, cough, and/or sputum production presents with acute onset and necessitates supplementing regular COPD medications with antibiotics for respiratory pathogens and/or steroids
Cardiovascular Related	An adverse event related to the heart and blood vessels or the circulation.
Heart Failure Event	A heart failure event is defined as any cardiovascular-related (including hypervolemia) Health Care Utilizations (HCUs) for any one of the following events.

**Medtronic Business Restricted**

**CONFIDENTIAL**

056-F275 Rev E Clinical Investigation Plan Template

# Reveal LINQ™ for COPD Study Clinical Investigation Plan

Version 5.0,  
1-DEC-22

Page 54 of 79

Medtronic

	

• Admission with primary diagnosis of HF

• Intravenous HF therapy (e.g. IV diuretics/vasodilators) or ultrafiltration at any one of the following settings: Admission with secondary/tertiary diagnosis of HF, Emergency Department, Ambulance, Observation Unit, Urgent Care or HF/Cardiology Clinic

 
Note: Only the Sponsor will be classifying Heart Failure Event relatedness.

Not Related	
Relationship to the device or procedures can be excluded when:
 

• The event is not a known side effect of the product category the device belongs to or of similar devices and procedures;

• The event has no temporal relationship with the use of the device or the procedures;

• The serious event does not follow a known response pattern to the medical device (if the response pattern is previously known) and is biologically implausible;

• The discontinuation of medical device application or the reduction of the level of activation/exposure – when clinically feasible – and reintroduction of its use (or increase of the level of activation/exposure) do not impact the serious event;

• The event involves a body-site, or an organ not expected to be affected by the device or procedure;

• The serious event can be attributed to another cause (e.g., an underlying or concurrent illness/clinical condition, an effect of another device, drug, treatment, or other risk factors);

• The event does not depend on a false result given by the device used for diagnosis (when applicable);

• Harm to the subject are not clearly due to use error;

*Medtronic Business Restricted*

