**Medtronic Business Restricted**

Chronic Obstructive Pulmonary Disease (COPD) is progressive and currently incurable and refers to a collection of diseases that lead to the key feature of irreversible airflow limitation and breathing related problems. It is characterized by loss of lung elastic recoil, small airway remodeling, a progressive decline in FEV1 (Forced Expiratory Volume), decreased lung emptying, and static and dynamic hyperinflation. Particulate exposure can lead to mucosal and glandular inflammation, increased mucous discharge and epithelial hyperplasia, and altered tissue repair in small conducting airways. COPD is the third leading cause of death worldwide, with an estimated prevalence of 175 million. Of those with COPD, 46% experienced at least one exacerbation within the previous year and 19% needed hospitalization.

Approximately 11% of those admitted for exacerbation die within 90 days, with half occurring during the hospitalization. 35% of those admitted for exacerbation are readmitted within 90 days. The financial burden of COPD is also evident, in that over \$32 billion was spent for COPD care in the United States in 2010 and it is expected to be close to \$50 billion in 2020^3. More than 70% of the spending is related to hospitalizations in the COPD patients due to acute exacerbations. Most COPD exacerbations are caused by infection, with other major triggers including outdoor and indoor particulate air pollution and weather. Confounding these metrics is the fact that there is much overlap in COPD with other concurrent disease. Approximately 1/3 of COPD patients die of cardiovascular disease and 1/3 of patients with cardiovascular disease have airflow limitation.

Reducing healthcare utilization associated with COPD patient management (i.e. short-term readmission and chronic disease management) is a critically important unmet need for patients, caregivers, and hospitals. Early detection, prevention, and treatment of COPD exacerbation would aim to reduce this high morbidity and cost.

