Respiratory distress is the primary driver for HF hospitalization and detection of respiratory distress provides an early indicator of ADHF. Respiratory symptoms such as breathlessness and orthopnea are significantly related to increased mortality and associated with worse clinical outcomes. The NOTICE-HF study, patient ambulatory respiration rate (RR) was monitored using an ICD or CRT defibrillator. Maximum, median, and minimum RR was significantly elevated prior to ADHF when compared to baseline. We hypothesize RR may be measured through subcutaneous thoracic space through the use of impedance or R-wave amplitude variations.

The LINQ™ for COPD study will collect and characterize Reveal LINQ™ derived data from patients with COPD by assessing the relationship between changes in LINQ™ derived data with COPD exacerbation events. The study will also collect information regarding COPD related clinical events during the same period.

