**Table 10: Adverse Event Classification Responsibilities**

What is classified?	Who classifies?	Classification Parameters
Relatedness	Investigator	Reveal LINQ™ system related, Reveal LINQ™ procedure related, Pulmonary Related, Cardiovascular related
	Sponsor	Reveal LINQ™ system related, Reveal LINQ™ procedure related, Pulmonary Related, Cardiovascular related, Heart Failure Event, COPD event
Seriousness	Investigator	SAE, Device Deficiency with SADE potential
	Sponsor	SAE, Device Deficiency with SADE potential, UADE, Complication/Observation
AE Term (Diagnosis)	Investigator	Based on presenting signs and symptoms and other supporting data
	Sponsor	MedDRA term assigned based on the term provided by Investigator
Death Classification	Investigator	Sudden Cardiac, Non-sudden Cardiac, Non-Cardiac, Unknown

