## 13. Data Review Committees

### 13.1 Event Adjudication Committee

At regular intervals, an Event Adjudication Committee (EAC) will review and adjudicate at a minimum, all events classified by the investigator or Medtronic as Pulmonary related and all AEs with a fatal outcome. The EAC will provide an adjudication for COPD event and a Complication or Observation classification for all AEs that are reviewed. The EAC will additionally provide a death classification for all AEs with an outcome of fatal. The EAC will consist of a non-Medtronic employed physicians that are not participating investigators for the study.

Medtronic personnel may facilitate and participate in an EAC meeting but will be non-voting members.

For all adverse events reviewed by the EAC, Medtronic will provide the EAC with the investigator's description and classification. The EAC is responsible for reviewing the investigator's assessment and supportive documentation (when available), reviewing applicable definitions, and determining final classifications for all adjudication parameters.

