### 14.3.3 Analysis Methods

Data from multiple study components will be collected in this study, of which the Reveal LINQ™ HF derived data is of the most interest. This includes subcutaneous electrocardiogram, impedance, temperature, accelerometer and patient activity measurements.

Descriptive statistics such as mean and standard deviation for continuous variables and count and proportion for categorical variables will be used to summarize the derived data from Reveal LINQ™ HF. The relationship between changes in LINQ™ derived data and COPD events per EAC adjudication will be evaluated. Specifically, for each subject that has experienced at least one COPD event per EAC adjudication, the average daily measurements of LINQ™ derived data before and after a COPD event will be plotted to identify patterns and signals related to the occurrence of the COPD event.

Baseline data such as demographics, medical history, physical exam (heart rate, blood pressure, weight, spirometry assessment, etc.), and blood measurements (Creatinine, BNP, NT-pro BNP, White Blood Cells and Eosinophils) will also be summarized using descriptive statistics.

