7.9.3 Analysis Methods

Data from multiple study components will be collected in this study, of which the Reveal LINQ™ HF derived data is of the most interest. This includes subcutaneous electrocardiogram, impedance, temperature, accelerometer and patient activity measurements.

Descriptive statistics such as mean and standard deviation for continuous variables and count and proportion for categorical variables will be used to summarize the derived data from Reveal LINQ™ HF. The relationship between changes in LINQ™ derived data and COPD events per EAC adjudication will be evaluated. Specifically, for each subject that has experienced at least one COPD event per EAC adjudication, the average daily measurements of LINQ™ derived data before and after a COPD event will be plotted to identify patterns and signals related to the occurrence of the COPD event.

In addition, exploratory survival analyses for time to first COPD event through 12-months of follow-up such as a Kaplan-Meier curve and Cox proportional hazards regression models with independent variables such as demographics and comorbidities will be included.

Each subject's time to first detected and adjudicated COPD event will be defined as the time from insertion date to the onset date of first COPD event. Subjects who have not experienced a COPD event through 12 months will be censored at:

- (1) their point of last contact, usable Reveal LINQ ICM interrogation or CareLink transmission if they occur before or at 12 months, whichever is later

or

- (2) 12 months (374 days) if their point of last contact, usable Reveal LINQ ICM interrogation or CareLink transmission go beyond 12 months.

Survival estimates and hazard rate with 95% confidence intervals will be reported.

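### Sponsor-classified Heart Failure Events play no part in the sensor analysis, so a sensor change around a COPD event that overlaps one can be attributed to COPD

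*Protocol*

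**What the plan says.** **Heart failure is defined, collected and classified.** CIP 12.4, Table 9 defines a Heart Failure Event as a cardiovascular-related use of health care: either an admission with heart failure as primary diagnosis, or intravenous heart failure therapy or ultrafiltration in one of several listed settings. The table adds that "Only the Sponsor will be classifying Heart Failure Event relatedness". Table 10 gives the sponsor's relatedness parameters, ending with "Cardiovascular related, Heart Failure Event, COPD event". CIP 12.1 collects "All Cardiovascular related AEs" and all serious events from consent.

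**The adjudication committee does not classify heart failure.** CIP 13.1: "The EAC will provide an adjudication for COPD event and a Complication or Observation classification for all AEs that are reviewed". It also classifies deaths.

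**The sensor analysis does not mention heart failure.** Under SAP 7.9.3, daily averages before and after a COPD event "will be plotted to identify patterns and signals related to the occurrence of the COPD event"; CIP 14.3.3 says the same. CIP 14.6 and SAP 7.4 set one further condition for an adjudicated COPD event to be used, namely device data on both sides of onset.

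**The rationale links the sensors to heart failure.** CIP 4.1 remarks that "there is much overlap in COPD with other concurrent disease". CIP 4.2 states that "Respiratory distress is the primary driver for HF hospitalization", that impedance moves inversely with thoracic fluid, and that respiration rate was raised before acute decompensation in an earlier study.

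**Entry criteria.** CIP 9.4 and SAP 5.2 exclude Class IV heart failure and a heart failure event in the previous 30 days.

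**The concern.** The primary objective is to relate sensor changes to subsequent COPD events, and CIP 4.2 and 6.2 say the data will feed methods for predicting exacerbations. If a COPD event falls close to a cardiac decompensation in the same subject, a fall in impedance or a rise in heart rate before onset may belong to either condition. The plan has a classification that would show where this happens, but the sensor analysis does not use it. A pattern partly driven by fluid overload could then be read as an exacerbation signature and carried into algorithm development. The absence of a hypothesis removes the type I error question. It does not remove the question of attribution, which is what the study sets out to explore.

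**Working it through.** **1. Can the two kinds of event coincide under the plan's definitions?**

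- A COPD event (CIP 5.1.1, Table 9; SAP 7.9.2) needs acute worsening of dyspnea, cough and/or sputum, plus added antibiotics and/or steroids. It does not require that heart failure be absent.
- A Heart Failure Event can be intravenous diuretic therapy during an admission where heart failure is a secondary diagnosis. It does not require that an exacerbation be absent.
- An admission for worse dyspnea treated with both steroids and intravenous diuretics could therefore meet both definitions.
- The two entry exclusions apply at enrolment. Patients with less severe, stable heart failure may enrol, and nothing in the analysis deals with decompensation during follow-up.

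**2. Does any planned analysis separate them?**

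| Place | Content | Uses the Heart Failure Event classification? |
|---|---|---|
| CIP 14.3.3, SAP 7.9.3 (plots) | Daily data around COPD events | No |
| CIP 14.6, SAP 7.4 | Data needed on both sides of onset | No |
| SAP 7.9.3 (Kaplan-Meier, Cox) | Time to first COPD event; demographics and comorbidities as example covariates | No; baseline heart failure could enter as a comorbidity, but sensor changes are not modelled |
| SAP 7.10 | All adverse events by MedDRA term, and a listing with onset dates | No; heart failure adverse events appear, but without this classification and without a link to the plots |

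**3. The plan's own figure.** CIP 14.4 and SAP 6: 60 subjects × 2 exacerbations per year × 1 year = 120 exacerbations; 120 × 0.50 = 60 COPD events. Both figures reproduce.

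**4. How many of the 60 might overlap?** The documents give no heart failure event rate and no overlap rate, so every input below is an assumption.

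*(a) Heart failure events independent of COPD events*, at rate h per patient-year, window W days either side of onset: p = 1 − exp(−h × 2W/365); expected overlaps = 60 × p.

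| h | W = 14 | W = 30 |
|---|---|---|
| 0.05 | 0.38%, 0.23 events | 0.82%, 0.49 events |
| 0.1 | 0.76%, 0.46 events | 1.63%, 0.98 events |
| 0.2 | 1.52%, 0.91 events | 3.23%, 1.94 events |
| 0.5 | 3.76%, 2.26 events | 7.89%, 4.73 events |

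Example: 0.5 × 60/365 = 0.0822; 1 − exp(−0.0822) = 0.0789; 60 × 0.0789 = 4.73. Independence may be too low, since step 1 shows that one episode can count as both.

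*(b) Overlap share assumed directly*: 5%, 10%, 20% or one third of 60 gives 3, 6, 12 or 20 overlapping events, leaving 57, 54, 48 or 40.

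The plots are specified for each subject with a COPD event, so in an affected subject's plot a heart-failure-driven change would appear undiluted, however rare overlap is across the study.

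**The case against.** The case on the other side is substantial.

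- **The study is exploratory and descriptive.** It has no hypothesis, and the plots serve "to identify patterns and signals related to the occurrence of the COPD event". The committee sees supporting documentation, and a heart failure episode that needed neither antibiotics nor steroids would not qualify as a COPD event. This stands, but adjudicating a COPD event does not rule out concurrent heart failure.
- **Heart failure events are reported.** A reader might infer that they are never used. That is wrong: SAP 7.10 tabulates and lists all adverse events with onset dates, so a close pair of events could be found by hand. The gap is confined to the sensor analysis.
- **Entry is more protective than it may look.** A reader might take Class IV as the only heart failure exclusion. The 30-day rule also applies, and the investigator may exclude conditions that would interfere with study procedures.
- **The sensor evidence is indirect.** The respiration finding came from ICD or CRT defibrillator recipients and the impedance finding from dialysis patients. For respiration measured subcutaneously the CIP offers a hypothesis. CIP 14.3.3 does not name respiration rate among the data of most interest, and only the ALLEViate-HF RAMware is described as calculating it. This limits the strength of the point but leaves impedance, which is named.
- **Heart failure is not shown to be the main rival explanation.** CIP 4.1 gives one-third figures for cardiovascular disease, not heart failure, and attributes most exacerbations to infection. What sets heart failure apart is practical: the plan already has a dedicated classification for it.
- **Table 9 is not at fault.** Its note says only who classifies. The omission lies in CIP 14.3.3 and 14.6 and SAP 7.4 and 7.9.3.

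**Conclusion.** The point holds as a cheap improvement. Heart Failure Events are classified and left out of the sensor analysis, the definitions allow overlap with COPD events, and the CIP's own rationale makes a heart-failure-driven sensor change plausible. Such a change near an overlapping COPD event *can* be attributed to COPD.

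A reader might go further and conclude that heart failure changes *are* being credited to COPD, or put a size on the bias: for example, a 10% to 20% overlap with a 1 SD change shifting a pooled average by 0.1 to 0.2 SD. The documents support neither. They give no overlap rate and no effect size, and they do not specify a plot pooled across events.

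The size is therefore unknown. On the plan's 60 COPD events, overlap is about 0.2 to 4.7 events under independence (assumed rates 0.05 to 0.5 per patient-year, windows of 14 to 30 days either side) and 3 to 20 events for assumed shares of 5% to one third.

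**What to change.** In SAP 7.9.3, and in line with it CIP 14.3.3:

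1. Mark every sponsor-classified Heart Failure Event on the before/after plots.
2. Keep all adjudicated COPD events in the main analysis.
3. As a sensitivity display, show the plots and any descriptive summaries with and without COPD events that have a Heart Failure Event inside a pre-stated window matching the plotted period. Neither document states how long that period is, so the SAP has to say.
4. Report the number of overlaps, separately for Heart Failure Events before and after COPD onset.

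The cost is one flag and one repeated display on data already collected, with no added committee work. The SAP needs revision in any case, since its analysis set names only the LINQ HF RAMware while CIP 14.3.4 also admits ALLEViate-HF.

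There are two downsides. The sensitivity set has fewer events. Excluding a COPD event because heart failure followed it also selects on later information, which fits poorly with an objective about changes before the event; item 4 and the retained full set address this. If overlap proves negligible, the display will show that and strengthen any COPD reading of the plots.
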